### **B. Statistical Considerations**

#### **a. Sample Size Justification:**

In performing the required sample size calculations, the authors assumed that potential cluster effects may be evident as a function of the individual surgeon. Because of this likelihood of cluster effects, we estimate the power of the study for change in post-operative pain that assumes an intra-class correlation (ICC) of at least 0.08 to inflate sample size estimates. This assumes 80% power to detect differences between groups with a 0.05 two-sided significance. Previous literature reports that in comparisons of opioid alone versus ketorolac with opioid the mean difference was observed to be 1.8 on the VAS (16). The widely accepted minimum clinically significant pain relief has been reported to be 1.3 (17). Detection of a 1.3 absolute difference in change in pain relief between groups requires 40 patients per group; detection of a 1.8 difference requires 20 patients per group consisting of eight and four (surgeons) respectively, assuming clusters of 10 subjects each. These calculations use an extremely high ICC which maximizes its accuracy. Because of the unknown ICC influence, a sensitivity analysis was performed assuming a non-contributory ICC of 0.08 which required a total sample size of 20 subjects per arm using the smallest clinically significant difference to detect.

Based on these calculations the largest sample required is 80 subjects. In order to preserve statistical power in the face of drop-outs and patient contact difficulties, the total sample size will be inflated by 10% such that the final projected sample size will be 88 subjects, or 44 per arm.

The next consideration for study design is the sample size calculations for delayed and nonunion in each group. Because earlier calculations have already incorporated ICC assumptions, the previous approach is still considered appropriate. Again drawing from higher level studies, the difference to detect has been determined to be 20.5% between groups (38). Using the same criteria from the previous calculations, an 80% power to detect differences between groups with a 0.05 two-sided significance will require a total sample size of 76, or 38 subjects per arm. If the ICC were to be changed to 0.01 detection of a 20.5% difference requires 40 patients per group with five clusters of sixteen patients for the total of 80 subjects. Given the ICC assumptions of the VAS calculations the authors have already attempted to incorporate a highly conservative sample calculation and included a 10% inflation for drop-outs.

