#### **A.4. Screening, Enrollment, and Post-operative Course**

##### *a. Screening, Informed Consent, and Randomization*

All subjects will be treated pre-operatively by his/her surgeon. Once the surgeon determines the patient will require a Kalish bunionectomy, he/she will review the patient's medical record to determine if the patient meets the study inclusion/exclusion criteria. If the investigator/surgeon determines that the patient meets study criteria, he/she will discuss the clinical trial with the patient. If the patient expresses interest in participating in the clinical trial, the investigator/surgeon and/or research fellow will complete a standard screening form to determine the patient's eligibility. All eligible patients will be given a copy of the informed consent form for review. A screening log will be maintained. If the patient has additional questions, he/she will be given the principal investigator's and research fellow's contact information.

On the day of the surgery (*Day 0*), the informed consent will be reviewed again with the patient by one of the investigators. If the patient decides he/she would like to enroll in this study, they will sign the informed consent form, and will be randomized in the pre-operative holding area to either ketorolac or placebo. The patient and surgeon will be blinded to which study drug he/she was randomized to. Baseline information will be recorded including baseline pain scores. Pain will be measured by both unidimensional and multidimensional instruments. This will include the McGill Pain Questionnaire-Short Form (MPQ-SF) and the visual analog scale (VAS). The VAS will be 10 cm in length with the end anchors, "no pain" and "worse possible pain".

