**Thus, the previously noted 88 total sample size (44 patients per treatment arm) was estimated to**

**be adequate to achieve study aims and goals.**

**b. Data Analysis**

**Outcomes and their Measurements**

*a. Primary Outcome*

All analyses will be calculated using Statistical Analysis Software (SAS, Worldwide Headquarters, Cary, NC) and will be based on the **intention-to-treat principle**.

The primary outcome of interest is pain measured on the second post-operative day, 48 hours ( $\pm 4$  hours) following surgery. This will allow the effects of anesthesia to subside following surgery. This will be well within the five day window in which the patient will be taking ketorolac post-operatively.

Pain will be measured by both unidimensional and multidimensional instruments. A blinded trained research fellow will contact patients by telephone and will administer the McGill Pain Questionnaire-Short Form (MPQ-SF) and instruct patients to fill out the visual analog scale (VAS). This will occur 48 hours ( $\pm 4$  hours) post-operatively. The VAS will be pre-printed in a diary that is given to the patient post-operatively. The VAS will be 10 cm in length with the end anchors, "no pain" and "worst pain possible". If patient compliance with the VAS is greater than 95%, then the VAS will be used for the primary analysis. As a back-up, the MPQ-SF will be utilized as the primary analysis. Regardless, sensitivity analyses will be conducted to verify the robustness of the results. The research fellow will also obtain the patient's post-operative pain medication consumption (including timing and dosages) and verbally confirm study protocol compliance during this telephone interview (Please refer to the variables collected section for full details; A telephone script is also included in this IRB application). Regression will be utilized to control for measured confounders, including timing of the telephone interview and last dose of post-operative pain medication. Standard regression model rules will be applied and a p-value  $\leq 0.05$  will be considered statistically significant in the final regression model.

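### The trial is sized on change in pain with no stated SD, but analyses the 48-hour score with no pre-specified role for the baseline score it collects

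*Combined protocol and SAP*

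**What the plan says.** All places are in the combined protocol and SAP.

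- **Sizing (B3.B.a, Sample Size Justification).** The calculation is framed as change: "we estimate the power of the study for change in post-operative pain", and then "Detection of a 1.3 absolute difference in change in pain relief between groups requires 40 patients per group". The operating characteristics are given as "This assumes 80% power to detect differences between groups with a 0.05 two-sided significance". The calculation "assumes an intra-class correlation (ICC) of at least 0.08 to inflate sample size estimates", with ten patients per surgeon. No SD appears for any pain measure, and the literature difference is quoted without one: "Previous literature reports that in comparisons of opioid alone versus ketorolac with opioid the mean difference was observed to be 1.8 on the VAS".
- **Analysis (B3.B.b, Primary Outcome).** "The primary outcome of interest is pain measured on the second post-operative day". This is a level at 48 hours; change from baseline is not mentioned. The primary regression is to control for measured confounders. Two are named, interview timing and the last dose of pain medication, in a list that is worded as open.
- **Baseline (A.4.a, Screening, Informed Consent, and Randomization).** "Baseline information will be recorded including baseline pain scores", by both VAS and MPQ-SF. The later section on other variables of interest lists pain scores among the data collected and says all variables will be compared between groups. No section gives baseline pain a defined place in the primary model.

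**The concern.** A power statement belongs to one outcome, one analysis and one SD. Here the sizing text speaks of change, the analysis text of a level, and the SD is missing, so a reader cannot tell which quantity the 40 per group refers to. Change and level have different variances unless the correlation between baseline and 48-hour pain is exactly one half (with equal SDs). The same 40 per group can therefore give quite different power.

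The collected baseline score is also the natural pre-randomisation covariate. If its use is left open, the final model can be chosen after the data are seen, and any available precision may go unused. With baseline in the model, taking change or the 48-hour score as the outcome gives the identical treatment effect, so the ambiguity about the outcome disappears.

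**Working it through.** **Inputs from the documents:** two-sided alpha 0.05; power 80%; difference 1.3 with 40 per group and 1.8 with 20 per group; ICC 0.08; clusters of 10; 80 patients inflated to 88. **Not in the documents, so assumed:** the SD; the correlation rho between baseline and 48-hour pain; equal SDs at the two times (needed only for the change score).

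**1. The plan's own figure.** With n per arm = 2(1.960 + 0.842)² SD²/δ² = 15.70 SD²/δ², the 40 per group cannot be reproduced without an SD. Solving backwards, SD = δ√(n/15.70). The design effect is 1 + 9 × 0.08 = 1.72, so 40 patients count as 40/1.72 = 23.26, and 20 as 11.63.

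| Stated pair | Implied SD, no design effect | Implied SD, design effect 1.72 |
|---|---|---|
| 1.3 with 40 per group | 2.08 | 1.58 |
| 1.8 with 20 per group | 2.03 | 1.55 |

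An SD of about 1.44 to 1.467 also fits everything if sizes are rounded up to whole clusters. It gives 20 per arm at 1.3 with ICC 0, which is how I read the sensitivity run. With the design effect it gives 33.1 to 34.4, rounded to 40, at 1.3, and 17.3 to 17.9, rounded to 20, at 1.8. None of this shows whether the SD is for change or for level. The inflation reproduces: 80 × 1.10 = 88.

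**2. Relative variances.** 48-hour score: 1. Change score: 2(1 − rho). 48-hour score adjusted for baseline: 1 − rho².

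**3. Power at 40 per arm.** Suppose 40 per arm gives exactly 80% for whichever quantity the design SD describes. Then power = Φ(2.802/√v − 1.960), where v is the variance of the analysed quantity relative to that one. A common design effect cancels. For example, with the SD for level and rho 0.3, adjusted: 2.802/√0.91 = 2.937, and Φ(0.977) = 83.6%.

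| rho | SD is for level: 48-hour unadjusted | adjusted | change score | SD is for change: 48-hour unadjusted | adjusted |
|---|---|---|---|---|---|
| 0 | 80.0% | 80.0% | 50.8% | 97.7% | 97.7% |
| 0.2 | 80.0% | 81.6% | 60.1% | 94.3% | 95.1% |
| 0.3 | 80.0% | 83.6% | 65.8% | 91.2% | 93.5% |
| 0.5 | 80.0% | 89.9% | 80.0% | 80.0% | 89.9% |
| 0.7 | 80.0% | 97.5% | 95.1% | 58.3% | 86.0% |

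The planned unadjusted 48-hour analysis falls below 80% only when the SD is for change and rho exceeds 0.5. If the 40 contains rounding slack (SD 1.45 needs 33.6), the threshold moves to 33.6/[2(1 − rho)] = 40, that is rho = 0.58.

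**4. Cost of adjusting.** One covariate inflates variance by 1 + 1/(N − 4): 1 + 1/76 = 1.013 at N = 80 and 1 + 1/84 = 1.012 at N = 88. Break-even at N = 80 is rho = √(1 − 1/1.0132) = 0.11. In 10,000 simulated trials at 40 per arm (SD 2.05, no clustering), power was 79.6% unadjusted and 78.9% adjusted at rho 0, and 80.4% against 83.6% at rho 0.3.

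**The case against.** The strongest reply is that little is wrong beyond loose wording. The sizing text never says change from baseline, and the background section on ketorolac describes the source of the 1.8 as an observed difference in VAS ratings. Change may simply mean a between-group difference. The covariate list is open, sensitivity analyses are promised and all variables are compared between groups, so baseline adjustment is permitted. Baseline is pre-operative bunion pain, while the outcome is acute surgical pain under analgesia. Their correlation could be low and the gain close to nil.

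All of this stands as a limit on the size of the point. It does not supply the missing SD, say what the SD would describe, or fix the primary model in advance.

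Two stronger readings are tempting, and the documents support neither.

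- A reader might infer that sizing and analysis target different treatment effects. They do not: baseline is scored before treatment, so randomisation makes the expected between-arm difference the same for change and for level.
- A reader might infer that the trial is underpowered, from the 51% to 66% in the change-score column or from about 58%. The first figures belong to a change-score analysis that the Primary Outcome section does not plan. The second arises if an SD back-solved without the design effect (about 2.05) is then combined with that design effect; nothing in the plan supports that pairing.

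**Conclusion.** The point holds as a gap in specification. The sizing text names change and gives no SD, the primary outcome is the 48-hour level, and the collected baseline has no pre-specified role, so the stated 80% power cannot be tied to the planned analysis. No loss of power in that analysis is demonstrated; it would need a design SD for change together with rho above 0.5.

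Baseline adjustment is a worthwhile, near-free improvement, with a gain that depends on a correlation the documents do not give: 0%, 4%, 9% or 25% of variance at rho 0, 0.2, 0.3 or 0.5. It should not be presented as a certain gain or as strictly free, because below a rho of about 0.11 there is a slight net loss. Nor does adjustment repair the sample-size text by itself: without an SD and its source the 40 per group remains unverifiable.

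**What to change.** - **Primary Outcome section:** define the primary analysis as a linear model of 48-hour VAS on treatment with baseline VAS as covariate. If the back-up instrument is used, take 48-hour and baseline MPQ-SF instead. Report the adjusted mean difference with its 95% CI.
- **Missing baseline scores:** add a simple rule, for example imputing the overall baseline mean without regard to arm, so that no randomised patient with a 48-hour score is lost.
- **Sample Size Justification:** replace change with this outcome, and state the SD, its source, whether it is for change or level, and any rho assumed. If rho is unknown, size on the unadjusted 48-hour SD and treat any gain from adjustment as reserve.

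Whether the two named covariates, both measured after randomisation, belong in the primary model is a separate question that this change leaves open. The cost is protocol and SAP wording plus one degree of freedom; the baseline data are already to be collected.

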#### **A.6. Randomization and Blinding**

Eligible patients will be randomized in the pre-operative holding area to either ketorolac or placebo by stratified permuted block randomization. Stratification will be by number of forefoot procedures (isolated Kalish bunionectomy versus Kalish bunionectomy plus additional forefoot procedures) and by unilateral versus bilateral (total of four possible strata: 1. Unilateral + Isolated Kalish Bunionectomy; 2. Unilateral + Kalish Bunionectomy with additional forefoot procedures; 3. Bilateral + Isolated Kalish Bunionectomy on one side; 3. Bilateral + Kalish Bunionectomy with any additional forefoot procedures. Any correlated cases will be accounted for in the analysis and are not common at this institution (but will be stratified in the event they do occur to help ensure balance between the study groups).

Study group allocation will be controlled by research pharmacy with sequentially numbered opaque sealed envelopes. This communication will occur entirely between the surgeon and research pharmacy. Allocation of ketorolac or placebo will be recorded on a "Randomization/Treatment" log that will be stored in a secure location with both opened and unopened randomization envelopes.

Access to this secure location will be controlled and locked. A coded master list will be kept in a locked and secured cabinet.

Patients, surgeons, anesthesiologists, and any assessors will be blinded. Only research pharmacy will not be blinded. Both ketorolac and placebo capsules and bottles and intra-venous preparations will appear exactly the same and will be prepared by research pharmacy. Assessors will be collecting data on post-operative pain and radiographic unions and will not be made aware of the patient's randomization results. In the event of an emergency or where the subject safety may be at risk, research pharmacy will unblind any necessary individuals to properly care for patients. In this event, the details of revealing the assigned study drug must be recorded in the subject's source documents.

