## **B6. RECRUITMENT AND CONSENT PROCEDURES**

### **Recruitment**

Previous long-term large clinical trials, through several NIH grants, have been conducted at our center. We will have access to a dedicated clinical research room as well as experienced and qualified research assistants who have successfully participated in numerous clinical trials. In addition, our facility hosts a dedicated two-year podiatric reconstructive and research fellowship and a podiatric medicine and surgery-36 residency.

Patients will be recruited from a large tertiary care institution which has one major primary foot and ankle clinic with satellite podiatry offices scattered throughout a metropolitan area. The demographics of the satellite patients are similar to those seen at the primary center for elective cases including bunionectomies. There are over 12,900 annual visits at the primary clinic and over 10,000 annual visits at the satellite clinics.

Surgical cases at our institution were reviewed for volume over the past two years. Adequate numbers of surgical cases were identified in both financial years 2007 and 2008 with 6 participating surgeons. An additional two surgeons have joined the staff in 2009 and volume is expected to either remain stable or increase. All eight surgeons are either board certified or board eligible by the American Board of Podiatric Surgery in both Foot Surgery and Reconstructive Rearfoot and Ankle Surgery. All are well versed in the indications and technique associated with the Kalish bunionectomy procedure. Please note that the power calculation also takes into account the estimated differences between surgeons by cluster analysis. Final analysis will also assess for differences between surgeons and surgeon experience and control for this by regression analysis if necessary.

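### The sample size is inflated for surgeon clusters although patients are randomised individually, so the stated 80% power is not this design's power; on the plan's own figures the error is conservative

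*Combined protocol and SAP*

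**What the plan says.** Section B3.B.a (Sample Size Justification) starts from the premise that "potential cluster effects may be evident as a function of the individual surgeon" and says that the calculation "assumes an intra-class correlation (ICC) of at least 0.08 to inflate sample size estimates". On error rates: "This assumes 80% power to detect differences between groups with a 0.05 two-sided significance". The results are: "Detection of a 1.3 absolute difference in change in pain relief between groups requires 40 patients per group"; and "detection of a 1.8 difference requires 20 patients per group consisting of eight and four (surgeons) respectively, assuming clusters of 10 subjects each". A sensitivity calculation then takes "a non-contributory ICC of 0.08 which required a total sample size of 20 subjects per arm using the smallest clinically significant difference to detect". The larger total, 80, is raised by 10% to 88, or 44 per arm. No SD is given anywhere in the section, and the design-effect formula is not written out.

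Section A.6 (Randomization and Blinding) says: "Eligible patients will be randomized in the pre-operative holding area to either ketorolac or placebo by stratified permuted block randomization". The strata are the number of forefoot procedures and unilateral versus bilateral surgery; surgeon is not a stratum. Section A.4.a and the Enrollment part of B6 agree that each consenting patient is randomised on the day of surgery.

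The Recruitment part of B6 names eight surgeons and says: "Please note that the power calculation also takes into account the estimated differences between surgeons by cluster analysis". It then plans to look for surgeon differences in the final analysis and to adjust by regression only if that proves needed.

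**The concern.** A factor of 1 + (m − 1) × ICC is the right inflation when all patients of a cluster sit in one arm, because between-cluster variance then goes straight into the treatment contrast. Here the patient is the randomised unit and nothing ties a surgeon to an arm. Surgeon is crossed with treatment, apart from chance imbalance, and surgeon effects largely drop out of the difference between arms. The power attached to 40 per group therefore belongs to a different design.

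What is at stake is the accuracy of the power statement for the primary endpoint. The clustering argument is offered as the reason to regard the sample size as safe, while the SD, which actually decides the power, is never shown.

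**Working it through.** **Inputs.** From B3.B.a: two-sided alpha 0.05, power 80%, ICC 0.08, clusters of m = 10, differences of 1.3 and 1.8, with 40 and 20 per group (eight and four surgeons in all), and 20 per arm at 1.3 in the sensitivity case. From A.6: individual randomisation. The SD is not stated and has to be back-calculated.

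**Step 1. Can the plan's figures be reproduced?** Not directly, without an SD, but they can be checked against each other.
- Design effect: 1 + (10 − 1) × 0.08 = 1.72.
- The sensitivity figure, read as uninflated, gives SD = 1.3 × √(20/2) / (1.96 + 0.84) = 1.47.
- At SD 1.467, n per arm = 2 × (2.80 × SD / difference)², which is 20.0 at 1.3 and 10.4 at 1.8.
- Times 1.72: 34.4 and 17.9. Rounded up to whole clusters of 10: 40 and 20 per arm, that is 4 and 2 clusters per arm, or 8 and 4 surgeons in total.

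Every VAS figure is matched, so the calculation behaves as a between-cluster one. If instead 40 is taken as exactly 1.72 times the uninflated n, SD = 1.3 × √(40/1.72/2) / 2.80 = 1.58. The implied SD is therefore about 1.47 to 1.58 cm.

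**Step 2. Power under individual randomisation.** If 40 per arm gives 80% with a design effect of 1.72, then without it power is Φ(2.80 × √1.72 − 1.96) = 95.7%, whatever the SD. The n for 80% is 40/1.72 = 23.3, so 24 per arm. From the sensitivity figure it is 20 per arm. (These use the normal approximation; the t-test adds about one patient per arm.)

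Power for 1.3 cm at 40 per arm, noncentral t:

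| SD (cm) | Basis | Power |
|---|---|---|
| 1.47 | implied by 20 per arm, uninflated | 97.5% |
| 1.58 | implied by 40 per arm with 1.72 | 95% |
| 2.0 | assumption | 82% |
| 2.1 | assumption | 78% |
| 2.2 | assumption | 74% |
| 2.5 | assumption | 63% |
| 3.0 | assumption | 48% |

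**Step 3. Does surgeon variance really cancel?** Simulation used 8 surgeons × 10 patients, ICC 0.08 and patients randomised individually without stratifying by surgeon. At SD 1.58, repeated runs gave a standard error of the treatment difference of 0.347 to 0.355. The unclustered formula gives 1.58 × √(2/40) = 0.353; the cluster formula gives 1.58 × √(2 × 1.72/40) = 0.463. Simulated power by t-test was 97.8% (SD 1.467) and 95.6% (SD 1.58); with surgeon as a fixed effect it was 96.9% and 95.0%. Type I error was about 5%.

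**Step 4. The duplicated ICC.** The main calculation and the sensitivity calculation both print ICC 0.08. For the same 1.3 difference they give 40 and 20 per arm. With the same ICC and cluster size both cannot be right. Step 1 works only if the sensitivity ICC is effectively zero.

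**The case against.** The strongest objection is that the error is harmless. Taking out the inflation raises power above 80%, the plan itself presents its calculation as conservative, N stays where it is, and the union endpoint is separately said to need 38 to 40 per arm. All of that stands as regards N. It does not rescue the stated figure: 80% is attached to a design the trial does not use.

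It is also fair to say that the plan never writes the design-effect formula, never says that surgeons are randomised, and never says that each surgeon will treat both arms. The first is an inference from figures that fit it exactly. The alternative, no inflation at all with an SD of about 2.03 to 2.08, contradicts both the stated inflation and the 20-per-arm sensitivity figure. As to the last, because A.6 does not stratify by surgeon, balance within a surgeon is expected but not guaranteed; the simulation allowed for this and the result held.

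A reader might infer that the primary comparison is underpowered. The documents do not support that. Power falls below 80% only if the SD exceeds about 2.05 cm, and it does so gradually (78% at 2.1, 74% at 2.2). No document gives an SD of that size, and the plan's own figures point to about 1.5. That risk, such as it is, comes from the missing SD and not from the design effect.

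Nor should a reader conclude that N can be cut to 20 to 24 per arm. Those numbers rest on a back-calculated SD without a source, and the union endpoint has its own stated requirement.

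**Conclusion.** The concern holds as a mismatch between design and method. The surgeon-cluster inflation does not apply to an individually randomised trial, and the stated 80% power for 1.3 cm at 40 per group is not the power of this design. On the plan's own figures it is about 95 to 98%, so the error is conservative. This rests on the inferred design effect of 1.72 and an implied SD of 1.47 to 1.58 cm.

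Two further defects in the same paragraph stand on their own: no SD or source is stated, so the true power cannot be fixed, and ICC 0.08 is printed for two cases that give different sample sizes. None of this shows that 88 patients are too few.

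**What to change.** In B3.B.a:
- Remove the between-cluster design effect and present the calculation as an individually randomised two-arm comparison.
- State the SD and its source for the outcome actually analysed. B3.B.a speaks of change in pain, while the Data Analysis section defines the primary outcome as pain at 48 hours; the SD must belong to whichever is used.
- Restate power for 1.3 cm at 40 evaluable per arm over a range of SDs, for example 1.5 to 3.0 cm. Do not choose an SD because it returns 80%.
- Correct the ICC in either the main or the sensitivity calculation.

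In B6, Recruitment, align the sentence on cluster analysis with the revised calculation, and replace conditional adjustment for surgeon with surgeon as a prespecified covariate in the primary model.

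Keep N at 88. The cost is a rewrite of one paragraph and two sentences; enrolment and data collection do not change, since the attending surgeon is already among the variables recorded.
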